Cover Page

Title: The Effects of Yoga on Psychological and Physiological Health in a Population Based Cohort

The main statistical analysis plan is on page 10 of the study protocol

Lund University IRB Approval Number: 2015/610

NCT Identifier Number: Not yet assigned

Document Date: 03/02/2018

PROJECT PLAN

YOGA PRESCRIPTIONS (YOGA PÅ RECEPT) – STUDY 2 **THE EFFECTS OF YOGA ON PSYCHOLOGICAL AND PHYSIOLOGICAL HEALTH IN A** **POPULATION BASED COHORT**

The general purpose of this study is to evaluate the benefits of yoga as a ‘mind-body’ practice, by measuring its effects on health-related psychological and physiological variables. We also aim to investigate whether a relation exists between subjective (psychological) and objective (physiological) measures, with a particular focus on stress as the primary outcome. Further, we intend to include measures of mindfulness, breathing and experiential avoidance – variables that may explain the mechanism by which yoga exerts its putative health-promoting effect. Similar to our previous research on the topic of yoga and health (Dnr 2014/906 & 2015/247) we expect that changes in stress, anxiety, sleep problems via yoga practice will lead to improved health outcomes among individuals reporting moderate to high levels of perceived life stress.

Background

Stress and worry in everyday life are common features of Western society, wherein demands to constantly achieve and not get ill are high - in the workplace, at school or at home. Evolutionarily, stress is a biological mechanism, necessary for all living creatures when being exposed to threats in the immediate environment, tapping the fight-or-flight-response via activation of the sympathetic nervous system (Kroese, 2000; Wallace, 2009). However, when exposed to stress during prolonged periods of time, the immune system is affected, leading to physiological as well as psychosocial problems (Kroese, 2000). The consequences of untreated high stress can not only turn into reduced job capacity, work roles conflicts, etc., but also into a mental illness such as an anxiety disorder or/and depression, which, in many cases, results in long periods lost from work (Hejbel, 2012).

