The primary purpose of this study is to evaluate the effects of yoga on: 1) psychological health, specifically measured as stress level, stress coping strategies, depression, anxiety, well-being, life harmony, diet, and sleep quality; and 2) physiological health, specifically measured as blood plasma and serum stress markers (e.g., hormones, inflammation), blood plasma stress-related indicators (i.e., metabolic and cardiovascular function), and non-invasive clinical measures of stress-related indicators (i.e, cardiovascular and autonomic nervous system function) including blood pressure, arterial stiffness (via pulse wave velocity), and heart rate variability (via electrocardiogram), as well as digestive health via gut microbiota fecal sampling. Further, we intend to explore whether any changes in coping strategies (breathing, mindfulness) as a result of yoga practice may correspond to predictable changes in well-being.

Method

Participants

We plan to conduct a randomized controlled field experiment. In order to properly evaluate the effects of the intervention statistically, we will recruit approximately 120 individuals (please see power analysis below). Study participants will be recruited primarily from the ongoing Malmö Offspring Study (MOS; Dnr 2012/594) which takes place at the Clinical Research Unit at Skånes University Hospital in Malmö (Klinisk Forskningsavdelning på Skånes universitetssjukhus i Malmö). MOS is an inter-generational study where all children and grandchildren of individuals in the Malmö Diet and Cancer Cardiovascular Cohort (MDC-CC; n=6103) are invited to participate. The MDC-CC is a population-based study that investigates the epidemiology of carotid artery disease (LU 51-90 and Dnr 2009/633; Melander, et al., 2009, 2012). Individuals participating in MOS who have indicated an experience of chronic stress during the past year will be contacted by the research team. Other individuals visiting the Clinical Research Unit and/or members of the community are also eligible to participate in the study according to the inclusion/exclusion criteria (please see below).

Procedure

1. Telephone and In-Person Recruitment and Screening

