At the follow up measurements, after the 5-week yoga practice, the participants will again be invited to the Clinical Research Unit at Skånes University Hospital in Malmö and have the same physiological measures taken as in the the first appointment. They will also fill out the same survey with psychological measures as they did at the first appointment. Breakfast will again be offered following completion of the measures. Finally, participants will be thanked for their participation in the research study.

Required sample size and a priori power analyses

The main statistical analyses will be regression analyses by estimating the models with full-information maximum likelihood (FIML) in AMOS software allowing to perform Intent-To-Treat analyses. The outcome variables will be all study variables calculated as the difference between pre-test and post-test scores.

Mediation models will be tested with the macro PROCESS by Preacher and Hayes (2008) which implements a bootstrapping procedure to create confidence intervals for indirect effects in the mediation model.

G*Power, 3. 1. 7 (Faul, Erdfelder, Lang, & Buchner, 2007) was used to calculate a priori power for analyzing main effects. Assuming that the effect is medium size ($f = 0.25$; see Cohen, 1988), a significance level is of $\alpha = .05$, and the power values of the F tests are .95, a total of $N = 105$ must be recruited.

Ethical Considerations

This research will follow the ethical guidelines regarding informed consent and confidentiality as specified by etikprövningslagen (2003:460). All participants will be informed of the study's aim and method, both orally and in writing, as well as sign an informed consent document prior to participation (see Appendix 4:1-4:2). They will be informed that their participation is completely voluntary and that they can discontinue participation at any time, without giving a reason. Contact information for the project leader will be provided to answer any questions.

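### Stress is called the primary outcome, but the main analysis treats every study variable as an outcome, with no designated stress measure, arm contrast or multiplicity rule

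*Combined protocol and SAP*

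**What the plan says.** Three places in the combined protocol and SAP bear on this.

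- The opening paragraph of the project plan describes the study "with a particular focus on stress as the primary outcome". It does not say which measure of stress.
- The Aims section is wider: "The primary purpose of this study is to evaluate the effects of yoga on: 1) psychological health", followed by the full psychological list and then the full physiological list. Stress level is one item of the first list. Blood stress markers and stress-related cardiovascular and autonomic indicators are in the second.
- The section on required sample size and power, which is the statistical analysis plan, states: "The outcome variables will be all study variables calculated as the difference between pre-test and post-test scores". It does not mention stress, name a contrast or give a multiplicity rule.

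The same section gives the only alpha in the document, as an input to the sample size: "a significance level is of $\alpha = .05$, and the power values of the F tests are .95". That calculation "was used to calculate a priori power for analyzing main effects", without saying main effects on which variable or between which groups.

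The Procedure section defines three arms: stress education plus yoga (SED_YOGA), yoga alone (YOGA) and control. The PSS appears in two forms, four items for eligibility and ten items as a study measure. Neither is named as primary.

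**The concern.** A primary outcome limits false positives only if the analysis plan says which variable it is, which comparison is made on it, and how the remaining results are to be read. Here the designation stops at the introduction. Followed as written, the main analysis gives the PSS, cortisol, LDL cholesterol and a coping scale the same standing, so a significant result on any of them could be presented as the main finding. With three arms there is a second free choice, between an overall test and particular contrasts. The power statement also belongs to no identified test, so a reader cannot say what the trial is powered to detect.

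**Working it through.** **The plan's own figure.** The documents give no family-wise error rate. Their one figure is the sample size: "Assuming that the effect is medium size ($f = 0.25$; see Cohen, 1988" and so on, ending in "a total of $N = 105$ must be recruited".

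- For a one-way F test of three equal arms on one difference score, the noncentrality is f² × N = 0.0625 × N, with 2 and N − 3 degrees of freedom.
- Power .95 then needs N = 252. At N = 105 the noncentrality is 6.56 and power is 61%. At the planned recruitment of about 120 it is 7.5 and power is 68%.
- N = 105 is matched under inputs that are not stated, for example a 3 × 2 group-by-time interaction with pre/post correlation of about .18. This does not show that the software run was wrong. It shows that the power statement cannot be attached to a test from what is written.

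**Counting the outcomes.** The count is mine; the documents do not give one.

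- Psychological: PSS, HADS anxiety, HADS depression, COPE, ISI, GHQ, HILS, LSS, KIMS, BEAQ and the breathing scale make 11. The diet items are asked once, so they have no pre/post difference and are left out.
- Physiological: LDL, HDL, triglycerides, creatinine, noradrenalin, adrenalin, renin and cortisol (8); fasting and 120-minute glucose (2); heart rate variability, blood pressure, pulse wave velocity and gut microbiota (4). These make 14.
- Total: 11 + 14 = 25. It is 24 if HADS is scored once, and about 39 if the 14 COPE strategies and two blood pressures are scored separately. Inflammatory markers and metabolic profiling are not counted.

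**Chance of at least one significant test if yoga affects nothing.** Assume one three-arm F test per outcome, each at .05.

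- Independent outcomes: 1 − .95^25 = .72. For 24 outcomes it is .71, and for 39 it is .86.
- Correlated outcomes, by simulation (25 null outcomes, 40 per arm, equal correlation between all pairs):

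| Correlation | At least one significant F test | At least one significant F test with the yoga arms together better than control |
|---|---|---|
| 0 | .72 | .48 |
| .3 | .61 | .33 to .36 |
| .5 | .47 to .50 | .26 to .27 |

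Ranges are the spread between separate simulation runs. The correlations are assumptions. At .7, with 24 outcomes and 35 per arm, the first figure is 33%. If questionnaires correlate at .5 to .7 among themselves and physiological measures at .1 to .3, it is 56% to 65%.

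**If one stress measure were fixed in advance.** The false-positive risk on that measure is 5% with one F test, about 9% with two unadjusted contrasts against control, and about 12% with all three pairwise contrasts.

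**The case against.** The best defence is that stress has a natural reading. The Aims separate stress level from biological markers, the PSS is the only listed scale of stress level, it comes first among the psychological measures, and four of its items decide eligibility. On that reading the error rate for the primary outcome is 5% to 12%, not 72%. Some variables also have a different role: mindfulness, breathing and experiential avoidance are presented as mechanisms, with separate mediation models, and a few items are called exploratory. This has force, but it remains inference. The analysis section still makes every variable an outcome, and the exploratory labels lead to no order of analysis. Some of those labels occur only where feedback to participants is discussed.

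Three stronger readings are tempting, and the documents support none of them.

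- *A false claim that yoga works is more likely than not.* This needs yoga to affect none of the outcomes, and it is not secure at correlations of about .5 or above. Counting only F tests that favour yoga, the figure stays below one half in every case tabulated. The use of .05 for each outcome is itself inferred from the power paragraph.
- *All three pairwise contrasts will be read on every outcome.* The plan does not say so; it refers only to F tests for main effects.
- *Pooling both yoga arms against control is simply the more powerful test.* At N = 120 and f = 0.25 its power is .78 against .68 for the overall F test, but only if both arms work equally well. With graded effects (SED_YOGA best, YOGA midway) it is .65 against .68, and if only SED_YOGA works it is .27 against .68. Pooling also mixes stress education with yoga.

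**Conclusion.** The concern holds in a limited form. The plan names a primary outcome in its introduction and does not carry it into the analysis, where no variable, contrast or multiplicity rule is designated. With about 25 outcomes, none affected by yoga and each tested once at .05, the chance of at least one significant overall test is about 72% under independence, 61% at correlation .3 and 47–50% at .5. About half of such trials or fewer would show a result favouring yoga. These figures rest on my outcome count, equal arms, assumed correlations and an alpha taken from the power paragraph. They describe the chance of some significant finding if any outcome may carry the conclusion, not the error rate of the PSS considered alone. The data would remain fully usable. What is at risk is the interpretation of a positive result.

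**What to change.** Before outcome data are analysed, add to the analysis section:

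1. The single primary outcome is the 10-item PSS total, analysed either as pre/post change or as the post-test score adjusted for baseline PSS. State which.
2. The primary between-arm comparison, named in advance, with two-sided alpha of .05 held across any further contrasts by a fixed sequence or Holm. Whether it is both yoga arms together against control, or each yoga arm separately against control, is the sponsor's choice, because the two answer different questions.
3. All other outcomes are secondary, with Holm or false-discovery-rate adjustment within the psychological and the physiological family, or are reported as exploratory.
4. A power statement for that primary test, giving the test, number of groups, degrees of freedom and any assumed pre/post correlation.

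The cost is a few sentences, with no new visits, measurements or participants. Restating power may show less than the planned .95 for the test chosen. Secondary outcomes become harder to declare significant: with 10 psychological and 14 physiological outcomes besides the PSS, the smallest p-value under Holm must reach .05/10 = .005 and .05/14 = .0036 respectively.

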Recruitment will be accomplished in two ways, 1) via telephone, and/or 2) in person. Telephone recruitment will be directed to participants in the Malmö Offspring Study (MOS) as described above. For individuals in MOS indicating a chronic experience of stress within the past year, information letters will be sent (see Appendix 3). Then they will be contacted by a person employed by the research project. During the telephone call, information about

the current yoga study, as described in the information letter in the Appendix 3 and Appendix 4:1 will be given, and the person will be asked if he/she is interested in participating. The telephone interviewer will also ask questions related to the inclusion/exclusion criteria described below. In-person recruitment will be directed to individuals visiting the Clinical Research Unit at Skånes University Hospital in Malmö who indicate high stress to the personnel. They will be orally given the same information as during the telephone interview previously described. Recruitment will take place over an approximate 2-month period.

Inclusion criteria:

1. A score on four items of the Perceived Stress Scale (PSS; Cohen et al., 1983) between 8-16, thereby indicating a current stress experience of at least moderate level (please see Appendix 5:12).
2. Ability to participate in the intervention during the time-period.
3. Comprehensive in Swedish (the intervention will be in Swedish).

Exclusion criteria

1. Ongoing yoga practice or any regular practice of yoga or meditation within the last 6 months.
2. Any known physical limitations that may prevent light physical activity (yoga postures).

When a person qualifies for the study, an appointment will be scheduled for him/her to come to the Clinical Research Unit at Skånes University Hospital in Malmö for the initial tests to be taken (see Measures below). The name of each participant will only be registered on a single master list in combination with a numeric code to ensure participant anonymity (please see Ethical Considerations below for further detail). Numeric codes will be used throughout the remainder of the study to identify participants. Additionally, the master list will provide the randomly generated number indicating which study group he/she is assigned to. Each person will be randomized at the individual level to one of the following conditions:

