The name of each participant will be registered on a single master list in combination with a numerical code. The list will be kept in a locked closet at the Clinical Research Unit at Skånes University hospital in Malmö, stored apart from other study documents. Numeric codes will be used throughout the research on all study documents to identify participants, in order to preserve confidentiality. Once data have been collected, the list with participants' names will be destroyed, ensuring that the identity of the participants will remain undisclosed. No individual names will ever be included in the data file. All study documents will be kept in locked closets, and contain no person names. The data used to assess the inclusion / exclusion criteria in the study (see above), will not be saved for participants excluded from the study. Any data collected from participants choosing to discontinue the study will be destroyed.

Bio-banking and laboratory analysis: Region Skåne biobank BD53 ([contact]) will be the biobank used in this study to store biological samples (i.e., blood serum and plasma, fecal samples). The biobank utilizes a freezer (-80 degrees) where biological samples are kept frozen until the time of analysis. Samples are not marked with a person's name or social security number, but with a numerical code that can only be connected to the participant (described above). Biological samples will be subsequently analyzed at the Department of Clinical Sciences, Faculty of Medicine, Lund University. The person responsible for bio-banking and laboratory analysis of biological samples is [name], Clinical Research Unit, Department of Clinical Sciences, Skåne University Hospital, Malmö, T: [name].

One possible risk of participating in this research is that individuals may experience some distress in participating in the study measurements. Blood sample collection and glucose tolerance testing require participants to come to their appointment in a fasting state. This

may cause some people to experience hunger and/or fatigue. To minimize discomfort, appointments are made in the early morning and blood collection will be among the first procedures performed. Participants will receive breakfast for free after the study measurements are complete.

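### The planned arm comparison uses pre/post differences and specifies no baseline covariate; adding the pre-test value of each outcome would usually gain precision at no cost

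*Combined protocol and SAP*

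**What the plan says.** The analysis plan is a short part of the section Required sample size and a priori power analyses. It names the method: "The main statistical analyses will be regression analyses by estimating the models with full-information maximum likelihood (FIML) in AMOS software". It then defines the outcomes: "The outcome variables will be all study variables calculated as the difference between pre-test and post-test scores". It lists no model terms, and baseline adjustment is not mentioned anywhere in the document.

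Three other parts of the protocol bear on the point:

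- Under Procedure, individuals are randomised to three arms. No stratification and no allocation ratio are stated.
- Under Measures and the second-appointment section, the physiological measures and the questionnaires are taken at both visits. The exception is the diet item, which is given only once, at the end.
- Under Inclusion criteria, entry requires a score on four items of the Perceived Stress Scale (PSS) "between 8-16, thereby indicating a current stress experience of at least moderate level". Stress is the stated primary outcome, and the 10-item PSS is completed later, at the first appointment.

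**The concern.** A change score subtracts the whole baseline value, as if each extra point at pre-test carried over as one extra point at post-test. Measurement error and five weeks of ordinary fluctuation usually make the real slope smaller than that. Subtracting too much adds noise to the arm comparison. It also means that an arm that happens to start higher appears to fall further with no treatment effect.

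The baseline values are already collected. What is at stake is precision on the main comparison, including the comparison on stress, that the trial could have without further participants or visits.

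**Working it through.** **The plan's own figure.** The protocol states that "a total of $N = 105$ must be recruited" for f = 0.25, alpha 0.05 and power 0.95. A three-arm one-way F test on change scores with these inputs needs 252, so 105 is not reproduced. Figures at or near 105 appear only with inputs the document does not state; for example, a three-arm group-by-time interaction with a pre/post correlation of about 0.18 gives 105. The number of groups, test family and correlation used are not given. The 105 is therefore unexplained, and nothing below depends on it.

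**Inputs.** From the protocol: about 120 participants planned, 105 in the power statement, three arms, two visits, f = 0.25, alpha 0.05. Assumed: equal arms (40 each at 120), no dropout, and pre/post correlation r = 0.3, 0.5 or 0.7.

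**Precision.** Let s0 and s1 be the pre-test and post-test standard deviations, and b = r x s1/s0 the slope of post-test on pre-test.

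- Error variance of the change score: s0² + s1² - 2·r·s0·s1
- Error variance after baseline adjustment: s1²(1 - r²)
- Difference between the two: s0²(1 - b)², which is zero only when b = 1

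With s0 = s1, the ratio of adjusted to change-score variance is (1 - r²)/(2(1 - r)) = (1 + r)/2.

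| r | variance ratio | information lost | standard error inflation, 1/√ratio - 1 | adjusted N matching change scores on 120 |
|---|---|---|---|---|
| 0.3 | 0.65 | 35% | 24% | 78 |
| 0.5 | 0.75 | 25% | 15% | 90 |
| 0.7 | 0.85 | 15% | 8% | 102 |

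A simulation with 40 per arm and 10,000 replicates gave losses of 33%, 24% and 14%.

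**Unequal standard deviations.** Information lost, from the general formula:

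| s1/s0 | r = 0.3 | r = 0.5 | r = 0.7 |
|---|---|---|---|
| 0.8 | 50% | 43% | 37% |
| 1.0 | 35% | 25% | 15% |
| 1.2 | 24% | 13% | 3% |
| 1.5 | 13% | 4% | 0% |

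For example, at s1/s0 = 1.2 and r = 0.5 the variances are 1 + 1.44 - 1.2 = 1.24 and 1.44 x 0.75 = 1.08, so the loss is 0.16/1.24 = 13%.

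**Power, three-arm F test.** Noncentrality is N x 0.0625/ratio, with 2 and N - 3 degrees of freedom for change scores (ratio 1) and 2 and N - 4 with adjustment. Here f is taken in change-score SD units and the standard deviations are equal.

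| N | change score | adjusted, r = 0.3 | r = 0.5 | r = 0.7 |
|---|---|---|---|---|
| 105 | 0.61 | 0.81 | 0.75 | 0.69 |
| 120 | 0.68 | 0.86 | 0.81 | 0.75 |

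The protocol does not say which SD standardises f. If it is the raw-score SD, power at 120 goes from 0.52 to 0.72, 0.68 to 0.81, and 0.89 to 0.93 at the three correlations.

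**Chance imbalance.** With 40 per arm, the baseline difference between two arms has standard error √(2/40) = 0.22 SD. The change-score estimate (post minus pre) is off by (b - 1) x imbalance. In the simulation, averaged over all randomisations with no treatment effect, both estimators centred on zero. Among replicates with a baseline difference above 0.2 SD (mean 0.32 SD), the change-score estimate was off by -0.22, -0.16 and -0.10 SD for r = 0.3, 0.5 and 0.7. The adjusted estimate was off by less than 0.01 SD.

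**Entry restriction on PSS.** Take r = 0.6 before selection and equal standard deviations. With no selection the loss is 20%. Selecting the top 30% directly on baseline reduces it to 6%. Selecting the top 30% on a separate screening score correlated 0.6 with baseline gives 16% to 27%, as the screening/post-test correlation runs from 0.36 to 0.60. All of these correlations are assumptions.

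**The case against.** The strongest reply is that the plan does not reject adjustment. It lists no predictors, not even arm, and a difference as outcome does not exclude a baseline covariate. That is right. A reader might infer that the trial has decided never to adjust, but the document is silent rather than opposed. What stands is that the text specifies the change score and nothing that would bring baseline into the model, so the analysis as written is unadjusted. Whether to adjust would otherwise be chosen after the data are seen.

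Three further inferences are tempting and not supported:

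- *The change score biases the arm effects.* Under individual randomisation it is unbiased on average. The error exists only given the realised imbalance, and it is the same (slope - 1) term that produces the extra variance, so it is not a second harm.
- *The loss is 15% to 35% in this trial.* The documents give no correlation and no SD. That range needs r of 0.3 to 0.7, equal standard deviations, and precision measured as inverse variance.
- *The loss is greater for stress because of the PSS entry range.* Narrowing the baseline spread alone shrinks the penalty s0²(1 - b)². Regression to the mean after selection on a separate score can enlarge it. The result depends on correlations the documents do not give.

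The gap between 0.68 and the stated 0.95 power is a separate sample-size question and adds no weight here.

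**Conclusion.** The point holds as a free improvement to a valid analysis. As written, the arm comparison fixes the post-on-pre slope at 1 and makes no stated use of baseline values beyond subtraction. In large samples baseline adjustment is never less efficient, and it is more efficient unless the true slope is exactly 1.

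Under assumed correlations of 0.3 to 0.7 and equal standard deviations, the loss is about 35% to 15% on the variance scale, or standard errors 24% to 8% larger. Over the SD ratios examined (0.8 to 1.5) it runs from near 0% to about 50%. For PSS the direction in which the entry restriction moves the loss is not established. The algebra is firm; the size in this trial cannot be known from the documents.

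**What to change.** In Required sample size and a priori power analyses, state that for each scalar outcome measured at both visits, the regression contains the arm indicators and the pre-test value of the same variable. The diet item is outside this rule because it has no pre-test value. So is the gut microbiota profile as a whole, which has no single pre-test score.

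The outcome may stay as the change score or become the post-test score. With both visits observed, the arm coefficient is identical, because subtracting the baseline from the outcome only lowers the baseline coefficient by 1. The planned software can fit the extra term.

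The four-item screening score need not be added. No gain has been shown for it. The Ethical Considerations section says only that screening data "will not be saved for participants excluded from the study", not that entrants' scores enter the analysis file.

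The cost is one sentence and one degree of freedom per model, with no new data, visits or participants.

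### The stated N = 105 for power .95 does not follow from the printed inputs for a three-arm F test on pre/post difference scores; the scaling of f and the G*Power routine must be stated

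*Combined protocol and SAP*

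**What the plan says.** All of this is in the combined protocol and SAP.

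- Under 'Required sample size and a priori power analyses', the analysis is given as "The main statistical analyses will be regression analyses by estimating the models with full-information maximum likelihood (FIML) in AMOS software", and the outcomes are defined thus: "The outcome variables will be all study variables calculated as the difference between pre-test and post-test scores".
- The same section says that G*Power "was used to calculate a priori power for analyzing main effects". The inputs are "Assuming that the effect is medium size ($f = 0.25$; see Cohen, 1988") and "a significance level is of $\alpha = .05"$. The result is "and the power values of the F tests are .95, a total of $N = 105$ must be recruited".
- Under 'Participants', recruitment rests on this calculation: "we will recruit approximately 120 individuals (please see power analysis below").
- Under 'Procedure', "Each person will be randomized at the individual level to one of the following conditions", followed by three arms: stress education plus yoga, yoga alone, and control.

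The document does not give the G*Power routine, the number of groups entered, the numerator df, the standard deviation to which f refers, a pre/post correlation, an allocation ratio or a dropout allowance.

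**The concern.** One difference score per participant and three randomised arms lead to a one-way comparison of three means with 2 numerator df. On the most direct reading of the printed inputs, that test needs more than twice 105 participants for power .95.

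This paragraph is the plan's only sample-size justification, and the recruitment target refers to it. As printed, it tells a reader that the trial has a 5% chance of missing a medium effect. Whether that is so depends on what f = 0.25 measures, and the plan does not say. Without that, nobody can tell which effect on stress, the primary outcome, the trial is able to detect, or how to read a non-significant result.

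**Working it through.** **Inputs.** From the plan: f = 0.25 (f² = 0.0625), alpha = .05, target power .95, three arms, one difference score per person, N = 105 stated and about 120 planned. Assumed, because not stated: equal allocation (35 per arm at 105, 40 at 120) and no dropout.

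**Step 1: attempt to reproduce N = 105, with f in difference-score SD units.** Noncentrality is lambda = N × f², with df = (2, N − 3). Power is the probability that a noncentral F exceeds the central 95% point.

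| N | lambda = N × 0.0625 | power |
|---|---|---|
| 105 | 6.56 | .612 |
| 120 | 7.50 | .676 |
| 159 | 9.94 | .80 |
| 252 | 15.75 | .95 |

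The stated figure is not reproduced. The smallest N for .95 is 251 as a regression with two group indicators, or 252 (84 per arm) with equal arms. The f detectable with power .95 is 0.389 at N = 105 and 0.363 at N = 120.

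**Step 2: a more favourable test.** A single-df contrast with the same f has power .718 at 105 and .775 at 120, and needs 210 for .95.

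**Step 3: repeated-measures routines with three groups and two time points, f = 0.25, power .95.** Here r is the pre/post correlation.

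| Effect tested | N at r = 0 | N at r = .5 |
|---|---|---|
| Group main effect | 129 | 189 |
| Time main effect | 108 | 57 |
| Group-by-time interaction | 129 | 66 |

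- The group main effect needs more as r rises, so no non-negative r gives 105.
- The time main effect falls from 108 at r = 0 to 96 at r = .1, so it passes 105 at a very small r. It tests the average change over all arms and does not compare them.
- The interaction gives 105 for r of about .18. At N = 105 its power is .90 (r = 0), .951 (r = .18) and .997 (r = .5).

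**Step 4: put the interaction on the difference-score scale.** With two time points, the interaction F test is the group F test on difference scores, with the same df (2, N − 3). G*Power uses lambda = N × f² × 2/(1 − r). Setting this equal to N × f_D², where f_D is the effect in difference-score SD units, gives

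f_D = f × √(2/(1 − r)).

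At r = .18: f_D = 0.25 × √(2/0.82) = 0.25 × 1.562 = 0.39. This agrees with the detectable f from Step 1.

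**Step 5: a third possible scale.** If f is in post-test SD units, with equal SDs at both times and equal baseline means, then f_D = f/√(2(1 − r)). That gives f_D = 0.177, 0.25 and 0.323 at r = 0, .5 and .7. Power at N = 105 is then .34, .61 and .84.

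**The case against.** The strongest reply is that the sponsor may have used the repeated-measures interaction routine, and that this is a legitimate way to power the planned analysis. Most of this stands. With two time points it is the same F test as the one on difference scores, so it cannot be set aside as a different analysis. Nor is the plan's reference to main effects decisive, since the sentence just before it concerns mediation and the phrase may only separate direct from indirect effects.

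What does not stand is that this makes the paragraph complete. The routine needs a pre/post correlation, and none is given. It returns 105 only near .18, against 129 at zero and 66 at .5. The f that it takes is also on a raw-score scale, so the effect detected with power .95 is about 0.39 on the outcome that the plan analyses.

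A reader might infer three stronger things that the documents do not support:

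- *That power is .61 whatever f means, so the chance of missing a medium effect is 32–39%* (1 − .676 and 1 − .612). That holds only for f in difference-score SD units. On the other scales, power at 105 runs from .34 to .997 over the correlations tried.
- *That 252 participants must be recruited.* That figure rests on the same scaling, and the effect worth detecting is the sponsor's judgement.
- *That the slip can be identified*, for example as a per-group number from a two-group test reported as a total. The documents do not settle where 105 came from.

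It is also fair to say that the plan recruits about 120 rather than 105, and that it makes no claim of equivalence or of no effect.

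**Conclusion.** The concern holds as a failure of the printed inputs to yield the printed result. For three arms and one difference score, f = 0.25, alpha .05 and power .95 do not lead to N = 105 unless a scaling of f and a pre/post correlation that the plan does not mention are supplied.

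With f in difference-score SD units, equal allocation and no dropout, power is .61 at 105 and .68 at 120. On both readings examined that compare the arms, N = 105 gives power .95 for f of about 0.39 on the difference score. The direct reading reaches this by solving for f, and the interaction reading by conversion at r of about .18. Dropout would lower these powers.

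The arithmetic is secure. Which scaling the sponsor intended is unknown, so the documents do not support an unconditional statement that the trial lacks power.

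**What to change.** Keep the target of about 120 and rewrite the sample-size paragraph. Name the G*Power routine, number of groups, numerator df, the SD to which f refers, and any assumed pre/post correlation. Then state:

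> For f = 0.25 in difference-score SD units, equal allocation and no dropout, the three-arm 2-df F test has power .61 with 105 analysed and .68 with 120; power .95 is reached only for f of about 0.39 (105) or 0.36 (120).

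If the interaction scaling was intended, say so, give the correlation with its source, and report the equivalent effect on the difference score (f of about 0.39 at r = .18).

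The cost is one corrected paragraph and, on the difference-score scale, a less favourable stated power. No extra participants are needed, and neither the design nor the analysis changes.
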